The initial protocol submitted and approved by the Duke IRB was intended to focus solely on the design and procedures for Aim 1 in order to address the three aims listed below in sequential order such that the findings from Aim 1 would be used to further develop the protocol design and procedures for Aim 2, and similarly the findings from Aims 1 and 2 will strengthen the approach to Aim 3.

This study will enroll up to 40-60 total participants for Aim-2 and Aim-3. While we anticipate that the screening blood draw will yield a number of screen failures, we expect that approximately 20-25 subjects will complete Aim-2 and 15-20 will complete Aim-3 of the study protocol.

Enrolled participants for Aim-2 will be asked to complete three study visits including the consent visit and two infusion study visits that will include hyperglycemic clamps and an infusion of Exedin-9. Each

infusion procedure will last 2 hours.

AIM-2: The primary outcome for visits 2-3 will be to measure the effects of Ex-9 on fasting glucose-stimulated insulin secretion before and after experimentally induced insulin resistance. The primary experimental variable for analysis will be C-peptide during the clamp. Mean values will be compared between the period of glucose only stimulation and glucose with Ex-9. For each subject in the active treatment arm data will be analyzed using 2-way ANOVA for repeated measures using time (0-60 vs 60-120 min) and treatment (Dex vs no Dex) as the two factors. Based on our previous studies we expect a significant time effect due to Ex-9. If there is an interaction with treatment we would conclude that experimental insulin resistance influences the fasting GLP-1 effect. Data from control subjects will be analyzed identically; here we expect no interaction, indicating that the fasting GLP-1 is a stable measure. In our previous study using Ex-9 during a glucose clamp, the average coefficient of variation in insulin concentrations at the conclusion of each step in the ramp was 30%. Using this estimate of between subject variation, detecting a 20% difference between subsequent steps in the GLP-1 ramp with a power of 80% and significance level of 0.05 will require 8 subjects.

Enrolled participants for Aim-3 will be asked to complete two study visits including the consent visit and one infusion study visit that will include a hyperglycemic clamp and an infusion of Exedin-9. The infusion procedure will last 2 hours.

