to target accrual and accrual rate. Describe interim analysis including plans to stop accrual during
monitoring. Phase I studies, include dose escalation schema and criteria for dose escalation with
definition of MTD and DLT.

AIM-2 – The primary outcome for visits 2-3 will be to measure the effects of Ex-9 on fasting glucose-stimulated insulin secretion before and after experimentally induced insulin resistance. The primary experimental variable for analysis will be C-peptide during the clamp. Mean values will be compared between the period of glucose only stimulation and glucose with Ex-9. For each subject in the active treatment arm data will be analyzed using 2-way ANOVA for repeated measures using time (0-60 vs 60-120 min) and treatment (Dex vs no Dex) as the two factors. Based on our previous studies we expect a significant time effect due to Ex-9. If there is an interaction with treatment we would conclude that experimental insulin resistance influences the *fasting GLP-1 effect*. Data from control subjects will be analyzed identically; here we expect no interaction, indicating that the fasting GLP-1 is a stable measure. In our previous study using Ex-9 during a glucose clamp, the average coefficient of variation in insulin concentrations at the conclusion of each step in the ramp was 30%. Using this estimate of between subject variation, detecting a 20% difference between subsequent steps in the GLP-1 ramp with a power of 80% and significance level of 0.05 will require 8 subjects.

AIM-3 – The primary outcome measure for this study will be the fasting GLP-1 effect. This will be defined as the difference in steady state glucose-stimulated insulin secretion with and without Ex-9. The difference will be expressed as a percentage of glucose stimulated insulin secretion without Ex-9, and serve as the primary variable for comparison among the lean, obese and diabetes cohorts.

Data & Safety Monitoring

Summarize safety concerns, and describe the methods to monitor research subjects and their data to
ensure their safety, including who will monitor the data, and the frequency of such monitoring. If a
data monitoring committee will be used, describe its operation, including stopping rules and frequency
of review, and if it is independent of the sponsor (per 45 CFR 46.111(a) (6)).

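### The 8-subject figure for Aim 2 does not follow from its printed inputs: it needs a within-subject SD or correlation that the plan never states

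*Combined protocol and SAP*

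**What the plan says.** The same power statement appears in the Research Abstract (AIM-2) and in Data Analysis & Statistical Considerations (AIM-2). Its variability input comes from an earlier clamp study in which "the average coefficient of variation in insulin concentrations at the conclusion of each step in the ramp was 30" per cent. The plan labels that number itself and sets the target in the same sentence: "Using this estimate of between subject variation, detecting a 20% difference between subsequent steps in the GLP-1 ramp with a power of 80" per cent. The conclusion is that a "significance level of 0.05 will require 8 subjects".

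The statement names no test and no sidedness. It gives neither an SD of differences nor a within-subject correlation.

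The Aim 2 data themselves are to be analysed by "2-way ANOVA for repeated measures using time (0-60 vs 60-120 min) and treatment (Dex vs no Dex) as the two factors". Design & Procedures (AIM-2) plans 10-15 subjects studied before and after dexamethasone (Dex) and 6-10 controls. The plan contains no other sample-size or power calculation; the Aim 3 paragraph has none.

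**The concern.** Successive steps of one ramp are measured in the same person. The precision of a step-to-step difference therefore depends on how much that difference varies between people, not on how much people differ from one another at a single step. The two quantities are linked only through the within-subject correlation. The plan presents 8 as the result of a between-subject CV, but that input cannot determine it.

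This matters because 8 is the only benchmark in the documents. A reader will set the planned 10-15 Dex subjects and 6-10 controls against it and conclude that the Dex arm has room to spare and the control arm is about adequate. The control arm deserves particular care: the plan expects no interaction there and would read that as evidence that the measure is stable. A null result carries that weight only if power is known.

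**Working it through.** **Inputs from the plan.** Difference 20%; CV 30%, described as between-subject; power 80%; alpha 0.05; stated answer 8.

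**Inputs the plan does not give.** Sidedness (two-sided taken as the main case, one-sided also shown), the test (paired t taken, normal approximation also shown), and the within-subject correlation ρ (varied).

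**Step 1: try to reproduce 8 by using 30% directly as the SD.**

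- Paired, two-sided, normal approximation: n = (1.960 + 0.842)² × (30/20)² = 7.85 × 2.25 = 17.7, so 18.
- Paired, two-sided, exact noncentral t: 20 (power 0.807).
- Paired, one-sided: 14 (normal), 16 (t).
- Paired t on the log scale, SD = √ln(1.09) = 0.294: two-sided 23 for a 20% rise or 16 for a 20% fall; one-sided 18 or 13.
- Two independent groups, two-sided t: 37 per group. This does not match a within-subject comparison and is shown only to confirm that it does not explain the 8 either.

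None of these gives 8. The paired lines also carry a hidden assumption: setting the SD of the difference equal to a per-step SD of 30% is the same as taking ρ = 0.5.

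**Step 2: treat 30% as what the plan calls it, the between-subject SD at each step.** With equal SDs at the two steps,

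SD of difference = 30 × √(2(1 − ρ)).

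Power is from the noncentral t with n − 1 degrees of freedom and noncentrality (20 / SD of difference) × √n, two-sided at 0.05.

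| ρ | SD of difference (%) | n for 80% power | Power with 8 |
|---|---|---|---|
| 0 | 42.4 | 38 | 21% |
| 0.5 | 30.0 | 20 | 37% |
| 0.7 | 23.2 | 13 | 55% |
| 0.8 | 19.0 | 10 | 73% |
| 0.85 | 16.4 | 8 | 84% |
| 0.9 | 13.4 | 6 | 95% |

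**Step 3: solve for what makes 8 correct.** With n = 8 and a two-sided paired t-test, 80% power needs a standardised difference of 1.156. Hence:

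- SD of difference = 20 / 1.156 = 17.3%.
- ρ = 1 − 17.3² / (2 × 30²) = 1 − 299.3/1800 = 0.83.

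The same steps for a one-sided t-test give a standardised difference of 0.978, an SD of 20.4% and ρ = 0.77. A two-sided normal approximation gives an SD of 20.2% and again ρ = 0.77.

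**Step 4: the planned arm sizes, for the same simple paired 20% comparison (two-sided t).**

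| ρ | n = 6 | n = 10 | n = 15 |
|---|---|---|---|
| 0.5 | 27% | 47% | 67% |
| 0.7 | 40% | 68% | 87% |
| 0.8 | 55% | 84% | 97% |

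Controls span n = 6 to 10 and Dex subjects n = 10 to 15.

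**The case against.** The strongest reply is that the sponsor may have used a high within-subject correlation and not written it down. Insulin responses to successive steps in one person may well track each other closely. At ρ of about 0.83, or about 0.77 with a one-sided test or a normal approximation, 8 is the right answer. This stands: it means the figure cannot be verified from the plan, not that it has been shown to be false. It does not rescue the sentence as printed, which credits the result to between-subject variation and leaves out the input that decides it.

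A reader might infer more than the documents support, in three ways.

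- **That the true requirement is 20 subjects and that 8 give 37% power.** Both numbers hold only at ρ = 0.5, which the plan does not state.
- **That the requirement is 37 per group.** That is an independent-groups figure, and the steps are compared within subject.
- **That neither planned arm reaches 80% power.** At ρ = 0.8 the Dex arm has 84% at 10 subjects and 97% at 15, and even 10 controls reach 84%. At ρ = 0.7 a Dex arm of 13 reaches 81%.

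It can also be said that the sentence sizes insulin differences between ramp steps, whereas the Aim 2 primary variable is C-peptide and the test of interest is the time-by-treatment interaction. That is true, and it limits what a corrected figure can show. It is a separate matter from whether the printed figure follows from its inputs.

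**Conclusion.** The point holds: 8 subjects does not follow from a 30% between-subject CV, a 20% difference, 80% power and alpha 0.05. The variance component named is the wrong one for a within-subject comparison, and the missing correlation moves the answer from 38 subjects at ρ = 0 to 6 at ρ = 0.9. Eight is correct only if the SD of the within-subject difference is about 17% or less (two-sided t), or about 20% or less (one-sided t).

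These results assume equal SDs at the two steps, a paired t-test, and 30% as the per-step SD. They concern the simple step comparison that the sentence describes, not the Aim 2 interaction. Underpowering of the 10-15 Dex subjects or the 6-10 controls is not demonstrated. What is established is that the plan's only power figure has no stated basis and should not stand as written.

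**What to change.** In both the Research Abstract and Data Analysis & Statistical Considerations (AIM-2):

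1. Replace the between-subject CV with the SD of the within-subject step-to-step difference from the sponsor's earlier clamp study.
2. State the test and whether it is one- or two-sided.
3. Recompute the number of subjects from those inputs and report whatever results. If the SD is about 17% or less (two-sided t), the 8 can stay.

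If that SD cannot be recovered, withdraw the claim that 8 subjects give 80% power. Alternatively, restate it as conditional on an explicitly assumed within-subject SD or correlation, with the range from 38 to 6 subjects for ρ from 0 to 0.9 beside it. The 30% should not simply be relabelled as the SD of the within-subject difference; the documents call it between-subject variation, and relabelling would bring in the ρ = 0.5 assumption unannounced.

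The cost is one sentence edited in two places. No extra subjects are needed, though the stated figure may become less favourable.

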AIM-3 – The primary outcome measure for this study will be the fasting GLP-1 effect. This will be defined as the difference in steady state glucose-stimulated insulin secretion with and without Ex-9. The difference will be expressed as a percentage of glucose stimulated insulin secretion without Ex-9, and serve as the primary variable for comparison among the lean, obese and diabetes cohorts.

Research Summary

State your primary study objectives

AIM-2: Determine the role of basal GLP-1 action on the β -cell response to insulin resistance. Healthy subjects will have fasting GLP-1 action determined with GLP-1r blockade before and after induction of experimental insulin resistance. We hypothesize that fasting GLP-1 action will increase to compensate for experimental insulin resistance.

AIM-3: The primary outcome measure for this study will be the fasting GLP-1 effect. This will be defined as the difference in steady state glucose-stimulated insulin secretion with and without Ex-9.

State your secondary study objectives

Please select your research summary form:

Standard Research Summary Template

This is the regular (generic) research summary template which is required for all regular applications (unless your protocol fits under the other research summary templates in this category). Use of these instructions is helpful for ensuring that the research summary contains all necessary elements.

Standard Research Summary

Purpose of the Study

Objectives & hypotheses to be tested

This protocol is funded by the Veteran's Administration and being led by [name] [name] in the Division of Endocrinology and the Duke Molecular Physiology Institute. The study will address the following three specific aims:

- 1. Determine the roles of fasting GLP-1 concentrations and alpha-cell secretion on insulin release. The first part of this aim will determine the threshold plasma concentration of GLP-1 that increases insulin secretion to test the hypothesis that fasting levels of circulating GLP-1 are insufficient to mediate β -cell secretion. The second part of the aim will determine whether the insulin response to specific amino acids is dependent on the α -cell release of GLP-1.

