- 2. **Determine the role of basal GLP-1 action on the β-cell response to insulin resistance.** Heal thy subjects will have fasting GLP-1 action determined with GLP-1r blockade before and after induction of experimental insulin resistance. We hypothesize that fasting GLP-1 action will increase to compensate for experimental insulin resistance.
- 3. Determine the role of basal GLP-1 action on fasting glucose regulation in lean, obese, pre-diabetic and diabetic subjects. A cross sectional study of age-matched subjects across the spectrum of glucose tolerance will be used to test the hypothesis that fasting GLP-1 action increases as β-cell function declines. Groups of lean, obese, pre-diabetic and type 2 diabetic (T2DM) subjects will receive exedin-9 during a graded glucose infusion. We hypothesize that the relative effect of GLP-1r blockade on insulin secretion will be greater with progression from normal to T2DM.

Initially, this study was to address these three aims in sequential order such that the findings from Aim 1 would be used to further develop the protocol design and procedures for Aim 2, and similarly the findings from Aims 1 and 2 will strengthen the approach to Aim 3. To that end, [name] has been able to address Aim 1 by collecting and analyzing data from another study with a similar protocol design. This IRB amendment is being filed to address the procedures for both Aim 2 and Aim 3.

Background & Significance

• Should support the scientific aims of the research

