Subjects will have two intravenous catheters placed, one in each arm: 1) for blood drawing, and 2) for the infusion of test materials. The arm for blood draws will be heated to maintain blood flow and arterialize venous blood. Four (4.0 ml) fasting blood samples will be taken at -15, -10, -5 and 0 minutes and then a variable infusion of 20% dextrose will begin to clamp the blood glucose at basal +3 mM for 120 minutes. This hyperglycemic clamp will be stabilized over 60 minutes and 4.0 ml blood samples will be taken every 5-10 minutes during this period to establish baseline insulin secretion and active GLP-1 levels. During these visits, participants will receive an infusion of Exendin-9 (750 pmol/kg/min) between the 60 and 120 minute time-points of the clamp procedure. For consistency, blood draws (4.0 ml) will occur every 5-10 minutes between the 60 and 120 minute time-points of both visit 2 and 3. Upon completion of the final 60-minute interval for the Ex-9 infusion, both the infusion and clamp procedures will be complete. One additional blood sample (1 ml) will be drawn post the assessment to be tested immediately with the YSI glucose analyzer to ensure glucose levels are within normal limits. **Visit 3** will occur at least one week later and will be a repeat infusion procedure identical to **Visit 2**. The total amount of blood collected during each of these visits will be a maximum of ~141 ml (~9.5 Tbsp).

We will aim to complete studies in 10-15 subjects before and after approximately one week of dexamethasone(Dex) treatment to induce insulin resistance. Insulin resistance in response to a short-course (4 mg daily) of supraphysiologic glucocorticoids is an established research procedure and is completely reversible over the course of exposure we are proposing. However, the rate of reversal is variable among subjects preventing a straight counter-balanced allocation to treatment (i.e. half of subjects getting Dex before the first study and half before the second). Therefore we will enroll 6-10 subjects as controls for effects of time and repeat testing. These individuals will have identical clamps with no dexamethasone at approximately 1 week intervals and will be determined at random by study staff.

AIM-3

Approximately 15-20 subjects will complete AIM-3 of the study and these participants will have two study visits – a baseline consent visit, and one infusion procedures.

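### The plan's only power statement, placed under Aim 2, sizes steps of a GLP-1 ramp that Aim 2 does not perform; the C-peptide interaction on which Aim 2 rests has no stated power

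*Combined protocol and SAP*

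**What the plan says.** The AIM-2 paragraph under Data Analysis & Statistical Considerations, which appears in the same words in the Research Abstract, makes C-peptide during the clamp the primary variable. It specifies a two-way repeated-measures ANOVA with period (first versus second hour) and treatment (dexamethasone or none) as factors. An interaction is to be read as an influence of insulin resistance on the fasting GLP-1 effect. Controls get the same analysis, and the expected lack of interaction there is to indicate that the measure is stable.

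The paragraph then cites a 30% coefficient of variation for insulin at the ends of ramp steps in an earlier Ex-9 clamp study and concludes: "detecting a 20% difference between subsequent steps in the GLP-1 ramp with a power of 80% and significance level of 0.05 will require 8 subjects".

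Design & Procedures, AIM-2, describes what is done at both infusion visits. A dextrose infusion will "begin to clamp the blood glucose at basal +3 mM for 120 minutes", and "participants will receive an infusion of Exendin-9 (750 pmol/kg/min) between the 60 and 120 minute time-points of the clamp procedure". On numbers it says "We will aim to complete studies in 10-15 subjects before and after approximately one week of" dexamethasone, with 6-10 further subjects as controls for time and repeat testing. About 20-25 subjects are expected to complete Aim 2.

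The GLP-1 concentration question belongs to Aim 1 under Purpose of the Study: "The first part of this aim will determine the threshold plasma concentration of GLP-1 that increases insulin secretion". The same section says that the investigator "has been able to address Aim 1 by collecting and analyzing data from another study with a similar protocol design" and that "This IRB amendment is being filed to address the procedures for both Aim 2 and Aim 3".

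**The concern.** The power sentence stands where the Aim-2 sample-size justification should be, so a reader will take 80% power with 8 subjects as support for the Aim-2 numbers. It differs from Aim 2 in design (ramp steps against a single-level clamp), in variable (insulin against C-peptide) and in contrast (one difference between steps against a difference of differences across visits). The application form asks in this section for power calculations and a sample-size justification. For the contrast that decides Aim 2 there is neither.

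Two things are at stake. Nobody can tell from the plan what change in the Ex-9 effect 10-15 dexamethasone subjects could detect. And the controls are the design's protection against time and repeat-testing effects, because the protocol rules out counterbalancing. With 6-10 of them, a non-significant interaction is weak evidence that the measure is stable.

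**Working it through.** **1. Plan's figure against Aim-2 design**

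| | Power statement | Aim 2 |
|---|---|---|
| Procedure | successive GLP-1 ramp steps | one clamp level (basal +3 mM), one Ex-9 rate, no GLP-1 infusion |
| Variable | insulin | C-peptide |
| Contrast | difference between two steps | period-by-treatment interaction |
| Number | 8 | 10-15 dexamethasone, 6-10 controls |

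No other power statement appears in the document, and none of the target numbers is linked to the 8.

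**2. Can the 8 be reproduced?** Inputs from the plan: CV 30%, difference 20%, power 80%, alpha 0.05. Sidedness and within-subject correlation ρ are not given. For a paired contrast, SD of the difference = 30·√(2(1−ρ)). With a two-sided paired t-test (noncentral t), the smallest n is:
- ρ = 0: SD 42.4, n = 38
- ρ = 0.5: SD 30.0, n = 20
- ρ = 0.7: SD 23.2, n = 13
- ρ = 0.8: SD 19.0, n = 10

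The lowest ρ at which n = 8 suffices comes from setting power at n = 8 to 80% and solving ρ = 1 − SD²/(2·30²):
- two-sided t: SD 17.3, ρ = 0.83
- one-sided t: SD 20.4, ρ = 0.77
- two-sided normal: SD = 20·√8/2.802 = 20.2, ρ = 0.77
- one-sided normal: SD = 20·√8/2.486 = 22.8, ρ = 0.71

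So 8 needs an undisclosed correlation of at least about 0.71 to 0.83, depending on method. The plan describes its CV only as between-subject variation ("Using this estimate of between subject variation, detecting a 20% difference between subsequent steps in the GLP-1 ramp").

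**3. Aim-2 interaction.** For each subject let D = (second-hour minus first-hour mean C-peptide at visit 3) minus (the same at visit 2). In a 2×2 within-subject ANOVA the interaction test is the one-sample t-test of D with n − 1 degrees of freedom. The table is in units of the SD of D, two-sided 0.05. The CI half-width is t(0.975, n−1)/√n, in observed SDs.

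| n | Group | Detectable at 80% | 95% CI half-width | P(non-significant) at a true 1.0 SD shift |
|---|---|---|---|---|
| 6 | controls, low | 1.43 | 2.571/√6 = 1.05 | 49% |
| 10 | controls, high; dexamethasone, low | 1.00 | 2.262/√10 = 0.72 | 20% |
| 15 | dexamethasone, high | 0.78 | 2.145/√15 = 0.55 | 5% |

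**4. Could controls reveal a drift that matters?** Assume equal SD of D in both arms and a control drift equal to the dexamethasone arm's own detectable effect. For group sizes that total the expected 20-25 completers, control power is:
- 10 dexamethasone/10 controls: 80%
- 12/8: 58%
- 15/10: 59%
- 14/6: 36%
- 15/6: 34%

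**5. Why the 8 does not transfer (illustration only).** Assume SD 30% for each period mean, one common correlation ρ among the four means, and a 20-point interaction. Then SD of D = 30·√(4(1−ρ)). At ρ = 0.834, the value that yields 8 for the ramp with a two-sided t-test, this is 24.5. The interaction then needs 14 subjects; power is 51% at n = 8, 64% at n = 10 and 84% at n = 15. At ρ = 0.5 it needs 38, and at ρ = 0.9 it needs 10.

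**The case against.** The planned 10-15 dexamethasone subjects all exceed 8, and the plan never uses 8 to set enrolment. The earlier study used Ex-9 during a glucose clamp, so its CV is related to the Aim-2 procedure, and insulin and C-peptide both bear on insulin secretion. This is a small mechanistic study, and the stability remark is worded as an expectation, with no formal equivalence rule.

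Much of this stands. The CV may inform planning, for instance of the within-clamp period effect, and the defect is one of justification and interpretation. But exceeding a number derived for another contrast shows nothing about the interaction, and the CV alone does not give the SD of a between-visit change. Although it is worded as an expectation, the sentence still says what an absent interaction would indicate.

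Two stronger readings are tempting. A reader might infer that Aim 2 is underpowered. The documents do not support that: they give no C-peptide SD, no between-visit correlation and no target change, and under the illustration above 15 subjects would have 84% power. A reader might also infer that 8 is a miscalculation. That is not shown either, because successive steps in one subject form a paired contrast and a correlation near 0.8 is possible there. What can be said is that an input is undisclosed.

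**Conclusion.** The point holds as a mismatch in the text, and no calculation is needed to see it: the 80%/8-subject figure is not a property of the Aim-2 design, and the interaction that decides Aim 2 has no stated power or detectable effect. Aim-2 power is unknown.

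A separate point is that non-significance in 6-10 controls cannot by itself show stability. A true shift of one SD would be missed about half the time with 6 controls and one time in five with 10. These figures assume approximately normal between-visit changes and a two-sided 0.05 test; they follow from the group sizes alone, so they do not justify the sample size until an SD is supplied. The drift range of 34% to 80% rests further on equal SDs in the two arms, and its upper end (10 and 10) is 80% by construction. The undisclosed correlation behind the 8 is secondary. This should be fixed, but it does not call the study's procedures or enrolment into question.

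**What to change.** Make these changes in the AIM-2 paragraph, both in the Research Abstract and under Data Analysis & Statistical Considerations.

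(a) Remove the 80%/8-subject claim as Aim-2 justification. The 30% CV may stay if labelled as insulin data from the earlier ramp study.

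(b) State instead: *The interaction is the within-subject change between visits in the Ex-9 effect on C-peptide. At 80% power and two-sided alpha 0.05 the detectable change is 1.00 (n=10) to 0.78 (n=15) in the dexamethasone arm and 1.43 (n=6) to 1.00 (n=10) in controls, in units of the SD of that change.* Add the SD from the sponsor's earlier clamp data, or show results over a stated range, so that the figures convert to C-peptide units. If the SD is derived from the single-visit SD of the Ex-9 effect, multiply by √(2(1−r)) and state the between-visit correlation r (factor 1.41 at r = 0, 1.00 at 0.5, 0.71 at 0.75).

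(c) Replace the stability sentence for controls with: *No interaction is expected in controls; the estimate will be reported with its 95% confidence interval, and a non-significant result alone will not be taken to show that the fasting GLP-1 effect is stable.*

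The cost is one calculation, replacement text in two places and one confidence interval in the report. Enrolment, procedures, endpoint and test are unchanged. The drawbacks are that the stated figure may look less favourable than the present one, that only a range can be given if the earlier data yield no C-peptide SD, and that stability may have to be reported as inconclusive.
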